8.3 Enrollment and Clinical Assessment

8.3.1 Obtaining Written Consent and Assigning Screening Numbers

Prior to any tests or procedures associated with this study, all information about the study should be provided to the subjects using a subject information sheet, and the informed consent form containing the subject name, signature, and date of signing will be obtained. A screening number will be assigned in order of written consent obtained from subjects.

The screening number will be denoted by for example, '00SXXX' (ex. 01S001) and means the following.

- '00': means site number
 - 01 : RS. University of Indonesia
 - 02 : RS. Islam Cempaka Putih
 - 03 : RS. MMA
- 'S': means screening
- 'XXX': order of subjects to be participating at each site

8.3.2 Demographic Information

At the screening visit (Visit 1), the followings will be investigated:

- Initial
- Month and year of birth (age)
- Gender
- Smoking history
- Drinking history

8.3.3 Questionnaire assessment

- Gastroesophageal Reflux Disease Questionnaires (GERD-Q) (See Appendix 3)
 - The subject will complete the GERD-Q at the screening visit (Visit 1) and Visit 2. The test results from Visit 1 will be used as the basis to determine eligibility for inclusion/exclusion.
 - The subjects who meet the inclusion criteria will complete the GERD-Q at Visit 3, Visit 4, and Visit 5.
- Quality of Life assessment (GERD-Health Related Quality of Life, GERD-HRQL) (See Appendix 4)
 - The subjects who meet the inclusion criteria will complete the GERD-HRQL questionnaire at Visit 2, Visit 3, Visit 4 and Visit 5.^[19, 20, 21]

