Study Methodology	
Subjects will be provided a written informed consent to participate in the study and then undergo any screening. If a subject is taking any drug that affects the gastric mucosa at the time of screening, the treatment will be start after washout period of up to 2 weeks. Subjects who meet all of the inclusion criteria and none of the exclusion criteria based on the screening test results will be randomized.
 
Overall, the subjects will receive treatment for a duration of 4 ~ 8 weeks., The subjects will take 1 tablet/capsule of the investigational product (IP) once daily (1 tablet of Fexuprazan 40 mg or 1 capsule Esomeprazole 40 mg according to randomization). Initially, the subject will received the IP for 1 week at Visit 2 (Day 0). Subject will visit the study site at Visit 3 (Day 7 ± 5 days) for early evaluation and will be prescribed for another 3 weeks of IP. Subjects will visit the study site at Visit 4 (Day 28 ± 5 days) to determine healing status through symptom relief. Healed subjects after 4 weeks of treatment will have a Safety Follow-Up (F/U) visit after 2 weeks, while unhealed subjects will continue with an additional 4 weeks of treatment. After unhealed subjects have completed a total of 8 weeks of treatment at Visit 5 (Day 56 ± 5 days), they will have a Safety F/U visit after 2 weeks. (This Safety F/U will be conducted over the phone. If necessary, additional examination and treatment may be performed according to the investigator's judgment.)

Figure 1. Study Schematic

Inclusion Criteria	
Subjects must meet all the following criteria:
 
 1) Male and female adults aged 18 to 60 years at the date of the written informed consent form. 2) Those who had experienced heartburn and/or acid regurgitation confirmed with: 
 ➢ GERD-Q Score >7 and ➢ People who have experienced heartburn symptoms > 3 days within the last 7 days, or ➢ People who have experienced acid reflux (symptom of acid reflux or back flowing of contents from stomach into the esophagus) > 3 days within the last 7 days 3) Those who could understand the provided information and able to fill out the questionnaire and subject diary. 4) Those who voluntarily decided to participate in the study and wrote the informed consent form.

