- 8) Pregnancy test will be performed with serum or urine pregnancy test will be performed at Visit 1. (Women who medically do not have child-bearing potential are exempt from the pregnancy test). If Visit 1 and Visit 2 are conducted on the same day, another pregnancy test (serum or urine test) should be conducted prior to IP administration even if the test result within 2 weeks before the date is available.
- 9) Eligibility of subjects will be assessed based on the results from Visit 2 (However GERD-Q result from Visit 1 will be used as the eligibility criteria).
- 10) Subjects who have not symptoms relief at Visit 4 will be prescribed the investigational product for treatment 2, and subject diary will be distributed to them. At Visit 5, treatment compliance will be checked, and subject diary will be collected only from those who have undergone Treatment 2.
(#: Subject diary completion will be checked at Visit 3, and appropriate training on diary keeping will be performed on the phone, if necessary.)
- 11) The Safety F/U will be conducted as a telephone visit within 2 weeks (\pm 5 days) from Last day of Visit 4 and Visit 5 only in subjects who complete all protocol-specific treatments, and the subjects may visit for additional tests or treatments based on the investigator's judgment.
- 12) If a subject decides to discontinue participation or is withdrawn from the study before completion, the Withdrawal visit procedures will take place within 2 weeks from the withdrawal decision. At the Withdrawal visit, the unused IPs or empty packaging will be returned, and the subject diary will be collected. However, assessment of Gastroesophageal Reflux Disease Questionnaire (GERD-Q)^{*)} and quality of life questionnaire (GERD-HRQL)^{*)} must be performed. If the patient refused to visit, above two Questionnaires can be done by telephone call and the document should be written on the EMR by the investigator.
- 13) Subjects who have not been healed after the Treatment 1 of investigational product administration will have an additional 4-weeks of treatment period (Treatment 2) with the same mode of administration.

[Abbreviations and Definition of Terms]

ADR	Adverse drug reaction
AE	Adverse event
AIDS	Acquired immune deficiency syndrome
ALT	Alanine aminotransferase, alanine
ANCOVA	Analysis of Covariance
APA	Acid pump antagonist
AST	Aspartate transaminase, aspartate
ATC	Anatomical therapeutic chemical
BUN	Blood urea nitrogen
BPOM	Indonesia Food and Drug Authority

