4.1 Study Period

- Study duration: Approximately 14 months from IRB approval to completion
- Study duration for each subject: 8-12 weeks
 - Screening period: Up to 2 weeks
 - Treatment period: Up to 4 weeks (unhealed subject will continue additional 4 weeks of treatment)
 - Follow-up period: For 2 weeks from the last dose

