8.2 Study Schedule Table

	Screening (wash-out)	Treatment 1			Safety F/U ¹¹⁾	Treatment 2 (Unhealed Subject after 4 Weeks of Treatment)	Safety F/U ¹¹⁾	Withdrawal Visit ¹²⁾
Visit	Visit 1 ¹⁾	Visit 2	Visit 3	Visit 4	Visit 4-1	Visit 5	Visit 5-1	
Protocol No.DW_DWP1401262001					30 / 55 page			Protocol Version, 2.1 Version date 2024-06-19

Schedule	Day-14~	Day 0	Day 7	Day 28	Day 42	Day 56	Day 70	
Window	-	-	± 3 day	± 5 day	± 5 day	± 5 day	± 5 day	
Informed consent	O							
Demographic survey	O							
Assessment on symptom questionnaire (GERD-Q) ²⁾	O	O	O	O		O ¹³⁾		O ^{*)}
Quality of Life assessment (GERD-HRQL)		O	O	O		O ¹³⁾		O ^{*)}
Medical and surgical history ³⁾	O	O						
Prior/concomitant medications ⁴⁾	O	O	O	O	O	O	O	O ¹²⁾
Vital signs ⁵⁾	O	O	O	O	O ¹¹⁾	O ¹³⁾	O ¹¹⁾	O ¹²⁾
Physical examination	O	O	O	O	O ¹¹⁾	O ¹³⁾	O ¹¹⁾	O ¹²⁾
Laboratory tests ^{6),7)}	O			O	O ¹¹⁾	O ¹³⁾	O ¹¹⁾	O ¹²⁾
Pregnancy test ^{6),8)}	O	O						
Inclusion/exclusion criteria ⁹⁾		O						
Prescription of IPs ¹⁰⁾		O	O	O ¹³⁾				
Return of IPs and check of treatment compliance ¹⁰⁾			O	O		O ¹³⁾		O ¹²⁾
Distribution of subject diary ¹⁰⁾		O	O	O ¹³⁾				
Collection of subject diary ¹⁰⁾			O	O		O ¹³⁾		O ¹²⁾
Adverse events			O	O	O	O	O	O ¹²⁾

- 1) Visit 1 and Visit 2 can be conducted on the same day.
- 2) Eligibility of subjects will be assessed based on the results from Visit 2 (GERD-Q result from Visit 1 will be used as the eligibility criteria). However, the results may be replaced with the test results obtained within 7 days prior to Visit 2, if available.
- 3) Gastrointestinal medical history and surgical history will be investigated at Visit 1 regardless of the time of previous occurrence and, for other medical history and surgical history, only those which occurred within 6 months from screening or are ongoing at screening and baseline will be investigated.
- 4) For prior medications, information on drugs administered within 4 weeks from the date of the written consent at Visit 1 will be collected. (Only Antacid and Prokinetic permitted as rescue drug)
- 5) Vital signs: After resting in a sitting position for 5 minutes or longer, blood pressure (diastolic/systolic), pulse rate, and body temperature will be measured.
- 6) The relevant tests can be replaced with the test results obtained from the same institution within 2 weeks from Visit 1, if available.

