- 7) Laboratory tests will be conducted to check the inclusion/exclusion criteria and assess the safety (Visit 1, Visit 4, Visit 5, Withdrawal visit, and Safety F/U). At Visit 1, a re-test may also be conducted once according to the investigator's judgment and, in such a case, evaluation will be based on the results of re-test.

① Hematology	WBC with differential count (neutrophil, lymphocyte, monocyte, eosinophil, basophil), RBC, hemoglobin, hematocrit, platelets
② Blood Chemistry	Random blood glucose, ureum, uric acid, AST, ALT, creatinine, total bilirubin
③ Blood Coagulation test	PT, INR, APTT
④ Urinalysis	pH, specific gravity, albumin, bilirubin, glucose, urobilinogen, ketone, nitrite, occult blood, microscopy (urine RBC, urine WBC)

- 8) Pregnancy test will be performed with serum or urine pregnancy test will be performed at Visit 1. (Women who medically do not have child-bearing potential are exempt from the pregnancy test). If Visit 1 and Visit 2 are conducted on the same day, another pregnancy test (serum or urine test) should be conducted prior to IP administration even if the test result within 2 weeks before the date is available.
- 9) Eligibility of subjects will be assessed based on the results from Visit 2 (However GERD-Q result from Visit 1 will be used as the eligibility criteria).
- 10) Subjects who have not symptoms relief at Visit 4 will be prescribed the investigational product for treatment 2, and

subject diary will be distributed to them. At Visit 5, treatment compliance will be checked, and subject diary will be collected only from those who have undergone Treatment 2.

(#: Subject diary completion will be checked at Visit 3, and appropriate training on diary keeping will be performed on the phone, if necessary.)

- 11) The Safety F/U will be conducted as a telephone visit within 2 weeks (\pm 5 days) from Visit 4 only in subjects who complete all protocol-specific treatments, and the subjects may visit for additional tests or treatments based on the investigator's judgment.

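### GERD-Q eligibility rests on the Visit 1 score alone, so a subject who already meets the success definition at Visit 2 can be randomised, which can mask a true deficit among symptomatic subjects

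*Combined protocol and SAP*

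**What the plan says.** Section 8.3.3 has the questionnaire completed twice before treatment: "The subject will complete the GERD-Q at the screening visit (Visit 1) and Visit 2". It then ties eligibility to the first of the two: "The test results from Visit 1 will be used as the basis to determine eligibility for inclusion/exclusion". Footnote 9 of the schedule table (section 8.2, and the same table in the synopsis) bases eligibility in general on Visit 2 results but makes an exception: "However GERD-Q result from Visit 1 will be used as the eligibility criteria". Footnote 2 repeats the exception and adds a permission: "However, the results may be replaced with the test results obtained within 7 days prior to Visit 2, if available".

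On timing, section 4.1 gives "Screening period: Up to 2 weeks", and the synopsis says that for subjects taking a drug that affects the gastric mucosa "the treatment will be start after washout period of up to 2 weeks". At the other extreme, footnote 1 states: "Visit 1 and Visit 2 can be conducted on the same day".

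Entry needs GERD-Q >7 plus heartburn or acid reflux on more than 3 of the last 7 days (section 3.2). Relief is GERD-Q <8 at Week 4, with no condition on the baseline score (sections 8.4.1.1 and 8.4.2.1). Non-inferiority is declared if the lower 95% bound for study minus control exceeds -0.1 (sections 9.2.3.1 and 9.3). The PPS is the primary analysis set (section 9.2.1).

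**The concern.** On a whole-number scale, the entry threshold (>7) and the success threshold (<8) are complements. A subject who scores 8 or more at Visit 1 and 7 or less at Visit 2 is eligible and already counts as relieved before taking any drug. That subject met the written criterion, so the exclusions for eligibility violations (section 9.1 for the FAS and PPS, section 13.5 for major deviations) do not apply.

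Subjects who would be counted as relieved in either arm whatever they received say nothing about the comparison. They move the observed difference towards zero. In a non-inferiority trial, that makes a real deficit among subjects who still had symptoms at the start of treatment harder to see.

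**Working it through.** **The plan's own figure.** Inputs from section 9.4.2: control 88.5%, study group 94.0%, margin -0.1, one-sided 2.5%, pooled Z-test, 53 per group. The mean rate is 0.9125. The pooled standard error is √(2 × 0.9125 × 0.0875 / 53) = 0.0549. The unpooled standard error is √((0.94 × 0.06 + 0.885 × 0.115) / 53) = 0.0546. Power = Φ((0.155 - 1.96 × 0.0549) / 0.0546) = 0.807, which agrees with the stated 0.80729. Dropout: 53 / 0.8 = 66.25, so 67 per arm and 134 in total. Both figures reproduce.

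**Can the case arise?** With up to 14 days between visits and a 7-day recall (Attachment 2), the two pre-dose scores can cover separate weeks. No section requires a score above 7 at Visit 2.

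**Does the symptom-day criterion prevent it?** The inclusion/exclusion row is ticked only at Visit 2, so this criterion may be judged there; the text is not explicit. If it is, item 1 or item 2 scores 3. The epigastric pain and nausea items are reverse-scored. A subject with neither complaint scores at least 3 + 3 + 3 = 9 and cannot be below 8. With those complaints on most days the total can be as low as 3. Of the 1,792 answer patterns with item 1 or 2 at 3, 237 total less than 8. This counts patterns and is not a prevalence. The criterion narrows the gap but does not close it.

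**Size.** Let f be the share already below 8 at Visit 2 who are also below 8 at Week 4 in either arm. The documents do not give f, so the values below are assumptions. The observed rate in an arm is f + (1 - f)p, and the observed difference is (1 - f)(pT - pC). Take a true 10-point deficit among symptomatic subjects, 78.5% against 88.5%, with 53 per arm. The chance of declaring non-inferiority comes from exact enumeration with a Miettinen-Nurminen score bound. The interval type is a choice made here, because the plan names only a chi-square or Fisher method.

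| Assumed f | Study rate | Control rate | Observed difference (points) | Chance of declaring non-inferiority |
|---|---|---|---|---|
| 0% | 78.5% | 88.5% | -10.0 | 2.48% |
| 5% | 79.6% | 89.1% | -9.5 | 2.91% |
| 10% | 80.7% | 89.7% | -9.0 | 3.42% |
| 20% | 82.8% | 90.8% | -8.0 | 4.74% |

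A normal approximation to the Wald interval gives 2.5%, 3.0%, 3.5% and 4.9%. If these subjects stay below 8 with probability 0.885 to 0.95 instead of 1, the approximation at f = 20% gives 4.7% to 4.8%.

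**A true advantage shrinks too.** At f = 20% the planned +5.5 points becomes 0.8 × 5.5 = +4.4. Power hardly changes (0.81 to 0.83, normal approximation), because the rates move closer to 100%.

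**The null hypothesis as written.** Section 9.4.2 defines both proportions over the whole treatment group. Set the overall difference to -0.10 at the f = 20% control rate (80.8% against 90.8%), and the same enumeration gives 2.46%. The nominal error holds.

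**The case against.** The rule is deliberate and is stated the same way wherever it appears. The share could be very small: it is zero for same-day visits, the symptom-day criterion limits it if checked at Visit 2, and footnote 2 lets a fresher result stand in. The only reason given for delaying treatment is washout. Acid suppressants are among the drugs washed out, and stopping them could raise Visit 2 scores, against any regression to the mean after selection on a high score. Nor is it certain that these subjects stay below 8: because of the reverse-scored items, less nausea or epigastric pain raises the GERD-Q.

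Most of this stands, and it limits the size of the problem. It does not remove it: footnote 2 permits replacement without requiring it, and only some subjects need to fall below 8 for the problem to exist.

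Three stronger readings are tempting, and the documents do not support them:

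- A reader might infer that the type I error is inflated. Under the null hypothesis in section 9.4.2 it is not. The 2.9% to 4.7% apply only when the deficit is defined among subjects symptomatic at Visit 2.
- A reader might infer a bias in favour of fexuprazan. Randomisation should balance these subjects between arms, so the effect is attenuation in both directions.
- A reader might infer that many subjects will have fallen below 8 by Visit 2. The documents give no share and do not settle the net direction of change between visits.

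**Conclusion.** The point holds as a loss of sensitivity. The plan collects a pre-dose score at Visit 2, sets it aside for eligibility, and counts as success an absolute score that some subjects may already have. Under assumed shares of 5% to 20%, a 10-point deficit among symptomatic subjects shows as 9.5 to 8.0 points, and the chance of missing it rises from 2.5% to between 2.9% and 4.7%. These figures rest on the assumed share, on those subjects being below 8 at Week 4 at the same rate in both arms, and on 53 evaluable subjects per arm. At the low end the effect is modest. The change is worth making because the data needed are already scheduled.

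**What to change.** **Preferred.** In section 8.3.3 and in schedule footnotes 2 and 9, require GERD-Q >7 at Visit 2 as well as at Visit 1 before randomisation. Same-day visits are unaffected and no procedure is added. The cost is some extra screen failures: to randomise 134, about 134 / (1 - f) subjects eligible under the present rule would be needed, which is 142, 149 or 168 at f = 5%, 10% or 20%. If the study has started, this is an amendment that needs IRB approval, and section 11.10 allows amendments then only in exceptional cases.

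**If eligibility is not changed.** Leave the PPS as defined. Report the number with Visit 2 GERD-Q <8 by arm, and pre-specify a supportive version of the primary comparison restricted to Visit 2 GERD-Q of 8 or more. The restriction uses a pre-dose value, so it does not condition on response to treatment. The cost is lower precision in that analysis. At f = 20%, 53 × 0.8 is about 42 per arm, and power under the planning rates falls from 0.81 to 0.71 (pooled Z-test). For that reason the restriction should stay supportive and should not be written into the PPS, which is the primary set.

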8.3.4 Medical/surgical history

Gastrointestinal medical history and surgical history will be investigated at the screening visit (Visit 1) regardless of the time of previous occurrence and, for other medical history and surgical history, only those which occurred within 6 months from screening or are ongoing at screening and baseline will be investigated. Any clinically significant medical conditions or abnormal conditions ongoing at screening will be investigated, and their diagnosis and persistence will be recorded on the case report form.

8.3.5 Prior/Concomitant Medications

Prior medications will be collected for the drugs administered within 4 weeks prior to the written consent at Visit 1, and concomitant medications will be collected for the drugs that have been administered since the administration of the IP.

8.3.6 Vital signs

The followings will be measured in a seated position after resting for 5 minutes at the screening visit (Visit 1), Visit 2, and Visit 4. Any clinically significant abnormalities prior to the administration of the IP will be recorded in the medical history section, and any clinically significant abnormalities after the administration of the IP will be recorded in the adverse events section.

- Blood pressure (systolic/diastolic)
- Pulse rate
- Body temperature

8.3.7 Physical examination

The investigator will measure the height, weight and the BMI at the screening visit (Visit 1), Visit 2, Visit 4, and Visit 5. Also, the subject's general condition including head, neck, heart, lung, abdomen, liver, skin, and extremities will be examined to check the health status and occurrence of any adverse events. Any significant change in physical examination will be reported as an AE.

8.3.8 Laboratory tests

Laboratory tests will be conducted to check the inclusion/exclusion criteria and assess the safety (Visit 1, Visit 4, Visit 5, Withdrawal visit, and Safety F/U). At Visit 1, a re-test may also be conducted once according to the investigator's judgment and, in such a case, evaluation will be based on the results of re-test. Hepatitis testing will be conducted at the screening visit (Visit 1) only.

① Hematology	WBC with differential count (neutrophil, lymphocyte, monocyte, eosinophil, basophil), RBC, hemoglobin, hematocrit, platelets
② Blood Chemistry	Random blood glucose, ureum, uric acid, AST, ALT, creatinine, total bilirubin
③ Blood Coagulation test	PT, INR, APTT
④ Urinalysis	pH, specific gravity, albumin, bilirubin, glucose, urobilinogen, ketone, nitrite, occult blood, microscopy (urine RBC, urine WBC)

Any clinically significant abnormalities before and after the IP administration will be recorded as medical history and AEs, respectively.

8.3.9 Pregnancy test

For women of childbearing potential, a pregnancy test with serum test or urine test will be conducted at the screening visit (Visit 1). If Visit 1 and Visit 2 are conducted on the same day, another pregnancy test (serum or urine test) will be conducted prior to IP administration even if the test result within 2 weeks before the date is available.

Women will be considered to be of non-childbearing potential if they:

- ① Have natural menopause (12 months of spontaneous amenorrhea; or follicle-stimulating hormone (FSH) >40 IU/L with 6 months of spontaneous amenorrhea)
- ② Are surgically sterile (hysterectomy, bilateral oophorectomy, bilateral salpingectomy, etc.)

8.3.10 Inclusion/exclusion criteria

Enrollment will be decided when all screening results of the subjects who provided written consent are assessed collectively.

8.3.11 Re-screening

Patients who do not meet the criteria for participation in this study may be rescreened. Patients may be rescreened once, at the discretion of the investigator (or designee), providing that the reason for screen failure was not due to a safety concern. If a patient is considered eligible for rescreening, this will be discussed with the sponsor prior to rescreening. Patients who are rescreened will be identified by a new patient number.

8.3.12 Randomization

The subjects who are determined eligible for participation in this study for meeting the inclusion/exclusion criteria will be randomized in a 1:1 ratio to one of study group and control group.

The randomization number will be denoted by for example, '00RXXX (ex. 01R001)' and means the following.

- '00': means site number.
 - 01: RS. University of Indonesia
 - 02: RS. Islam Cempaka Putih
 - 03: RS. MMA
- 'R': means randomization
- 'XXX': order of randomized subjects

